4.17.11.2 Assay Positivity by Visit

The number and percentage of subjects with positive results at each visit will be presented by baseline status (such as screen positive, negative etc) and by treatment group. The positivity analysis for ELISpot will be summarized for the overall treatment of BIIB111 as well as with respect to either REP1 or AAV2.

4.17.11.3 Assay Treatment-emergent Analysis by Visit

The number and percentage of subjects with a positive result will be further tabulated by treatment-emergent status (see definition below, treatment-emergent and non-treat-emergent positive) by, visit, period, surgery windows, and surgery windows combined.

A treatment-emergent positive result is defined as follows for ADA and Nabs:

- A post-baseline result that is positive when the baseline result is negative.
- A post-baseline result that has a titer greater than or equal to 4 times the baseline titer when the baseline result is positive, while titer values are available at both baseline and post-baseline visits.

For ELISpot, the treatment-emergent positive for each analyte is defined as a post-baseline result that is positive when the baseline result is negative. If any of the 3 REP1 analytes is treatment-emergent positive, it is a treatment-emergent positive for REP1. The treatment-emergent positive for AAV2 is defined as a post-baseline result that is positive when the

baseline result is negative for the AAV2 analyte. If either REP1 or AAV2 is treatment-emergent positive, it is a treatment-emergent positive for the overall treatment of BIIB111. The treatment-emergent analysis for ELISpot will be summarized for the overall treatment of BIIB111 as well as with respect to either REP1 or AAV2.

If either the valid baseline samples (see definition above, prior to surgery or Day 1) or valid post-baseline samples at a particular visit are not available, the subject will be assigned as missing for treatment-emergent status at that particular visit and excluded from the treatment-emergent assessment. The remaining available valid baseline samples and post-baseline assessments will be tabulated and contribute to the positive/negative overtime summary mentioned in 14.15.11.2. Invalid sample results include but are not limited to “Quantity Not Sufficient”, “No Results”, etc and will be deemed missing.

For analyses on treatment-emergent immunogenicity, period 1 baseline will be used to derive the change from baseline for data of period 1 visits (before 2nd eye injection) and period 2 baseline will be used to derive the change from baseline for data of period 2 visits (post 2nd eye injection).

4.17.11.4 Relationship Between Immunogenicity Assay and Safety

The relationship between the immunogenicity assays (ADA, Nab and ELISpot) and selected adverse events will be assessed. These adverse events include ocular inflammation-related adverse events, visual acuity reduced-related adverse events and hypersensitivity-related adverse events. The number and percentage of post-treatment (treatment-emergent) ocular inflammation-related adverse events, visual acuity reduced-related adverse events and hypersensitivity-related adverse events (based on the adverse event data), as well as the number and percentage of eyes with a decrease from baseline of ≥ 15 letters in BCVA at Month 12 (based on the visual acuity assessment data) will be summarized by (1) subjects with negative assay at period 1 baseline; and (2) subjects with positive assay at period 1 baseline; and (3) subjects with at least one treatment-emergent positive assay at any visit during the study; and (4) subjects with no treatment-emergent positive assay during the study. In (3) and (4), to determine the treatment-emergent positivity, the period 1 baseline will be used to calculate the change from baseline for data in period 1 and period 2 baseline will be used to calculate the change from baseline for data in period 2.

The analyses will be conducted by eye, by period and surgery window. It will be repeated by AE severity (mild, moderate and severe) and by AE time to onset (≤ 30 days and > 30 days post-surgery). If an AE has more than one occurrence with an onset ≤ 30 days and another > 30 days, the AE will be reported in both ≤ 30 days and > 30 days' time to onset categories.

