4.3 Definitions

Study Eye 1 (SE1) is defined as the first treated eye (within GEMINI or in an antecedent clinical trial). **Study Eye 2 (SE2)** is defined as the second treated eye (irrespective of whether the first eye was treated in GEMINI or in an antecedent clinical trial). Subjects whose first eye is treated in an antecedent study will contribute to Period 2 only (except for the immunogenicity analyses), where Study Eye 1 is the eye treated in the antecedent study and Study Eye 2 is the eye treated in GEMINI.

Period 1 starts on the day of the surgery of the first treated eye and ends on the day prior to the day of the surgery of the second treated eye. **Period 2** starts on the day of the surgery of the second treated eye.

Baseline Value of Period 1/2 is defined as the last non-missing value prior to treatment of the respective period. Baseline of each period for each eye will be used to calculate the change from baseline for the data in the same period and same eye. For example, period 1 SE1 baseline will be used to calculate the change from baseline for all the data of SE1 in period 1, whereas period 2 SE1 baseline will be used to calculate the change from baseline for all the data of SE1 in period 2.

For immunogenicity, baseline will be defined separately in [Section 4.17.11](#).

Analysis day for all the post-baseline visits will be calculated as the date of the post-baseline visits minus the corresponding injection date, depending on which baseline that was used.

For the 6 subjects whose first eye was treated in the antecedent study (Subjects [REDACTED], [REDACTED], [REDACTED]), only period 2 data are collected in GEMINI. Therefore, only period 2 data will be presented for these 6 patients.

Change from Baseline is defined as the difference of the value of an assessment at the considered visit from the baseline value of the corresponding period.

Duration is measured in days and is calculated as end date – onset date + 1.

Injection dates of SE1 and SE2 will be coded **Day 0** for the Period 1 and Period 2 respectively.

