4.4 Data of Subjects with First Eye Treated in an Antecedent Study

For the 6 subjects who received timrepigene emparvovec treatment in their first eye in an antecedent study, the data from the antecedent study will not be included in the analyses presented in the Clinical Study Report (CSR).

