4.17.11.1 Baseline Definition

As the second eye treatment in Period 2 in GEMINI may potentially increase the risk of a subject developing an immune response against the therapeutic product, BIIB111, we define two different types of baselines to evaluate the treatment emergent immune response, anchored to the time when the first eye was treated, and when the second eye was treated, respectively. The definition is as below.

Period 1 baseline is defined as the last available value prior to surgery of the first eye. For subjects without any assessments prior to surgery of the first eye, Day 1 sample will be used as baseline. If neither assessment prior to surgery of the first eye nor Day 1 sample are available, the period 1 baseline is set missing.

Period 2 baseline is defined as the last available value within 10 weeks prior to the surgery of the second eye. For subjects without any assessments within 10 weeks prior to surgery of the second eye, Day 1 sample post-second eye surgery will be used as baseline for period 2. If neither assessment prior to surgery of the second eye nor Day 1 sample are available, the period 2 baseline is set missing.

Note that the immunogenicity data is collected as one record per subject per visit.

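### No planned summary groups Period 2 safety events by assay status at second-eye dosing

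*SAP*

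**What the plan says.** SAP 4.17.11.4 tabulates selected adverse events (ocular inflammation, reduced visual acuity, hypersensitivity) and eyes that lost at least 15 letters at Month 12 under four subject groups. The first two are "1) subjects with negative assay at period 1 baseline; and (2) subjects with positive assay at period 1 baseline". The third is "3) subjects with at least one treatment-emergent positive assay at any visit during the study". Its complement, the last group, is "4) subjects with no treatment-emergent positive assay during the study". On layout: "The analyses will be conducted by eye, by period and surgery window".

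SAP 4.17.11.1 sets up two immunogenicity baselines and gives its reason: "As the second eye treatment in Period 2 in GEMINI may potentially increase the risk of a subject developing an immune response". The Period 1 baseline is the last value before first-eye surgery. For the other, "Period 2 baseline is defined as the last available value within 10 weeks prior to the surgery of the second eye". In both cases a Day 1 sample is the fallback. Within 4.17.11.4 the Period 2 baseline has one use: it is the reference value for deciding whether a Period 2 result is treatment-emergent.

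For ADA and Nabs, SAP 4.17.11.3 calls a result treatment-emergent if it is positive after a negative baseline, or if the titer reaches at least 4 times a positive baseline. An ELISpot analyte must go from negative to positive.

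On the six subjects whose first eye was treated in an antecedent study, SAP 4.3 says they "will contribute to Period 2 only (except for the immunogenicity analyses". The same section later limits what is presented for them to Period 2 data. SAP 4.4 says "the data from the antecedent study will not be included in the analyses presented in the Clinical Study Report".

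**The concern.** SAP 3.6 singles out the immunological profile as the main worry when a gene therapy is given again. For Period 2, the natural safety question is whether subjects who already carry an immune response when the second eye is dosed have more inflammation or vision loss afterwards than those who do not. The plan defines the variable that answers this, the Period 2 baseline, but does not use it as a grouping in the table that links assays to safety.

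Period 2 events are instead set against a status fixed before the first eye. In the long surgery window, that sample is more than 12 months old by then. A subject who is negative before SE1, converts, and is still positive at SE2 belongs to group (1) for his second-eye events. If such subjects have a higher Period 2 risk, they raise the group (1) rate, and the contrast with group (2) shrinks.

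A smaller, separate matter is that the six antecedent subjects may have no usable Period 1 baseline, depending on which of 4.3 and 4.4 governs.

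**Working it through.** The plan states no figure to reproduce: SAP 4.2 plans no formal comparison, and neither document gives a conversion rate or an event rate by assay status. The check is therefore one of classification, followed by an illustration on assumed rates.

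**Step 1. Does any group fix status at the Period 2 baseline?** Take four titer levels (negative, 10, 40, 160) at four times: Period 1 baseline, post-baseline in Period 1, Period 2 baseline, post-baseline in Period 2. Apply the ADA/Nab rule to every combination. Every group contains both statuses:

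| Group | Can be positive at Period 2 baseline | Can be negative at Period 2 baseline |
|---|---|---|
| (1) | converted after SE1, persisted | never converted, or converted and reverted |
| (2) | stayed positive | reverted |
| (3) | converted before SE2 dosing | converted only after SE2, possibly after the event |
| (4) | stable positive, no 4-fold rise | never positive |

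Crossing (1)/(2) with (3)/(4) is not planned. It would fix the status in only one of four cells: negative at Period 1 baseline and never treatment-emergent implies negative at Period 2 baseline. Even that needs a Period 2 baseline sample taken before surgery, not the Day 1 fallback.

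**Step 2. Do other outputs supply the grouping?**
- 4.17.11.2 shows positivity by baseline status without saying which baseline, and without adverse events.
- 4.17.11.3 shows treatment-emergent status by visit, period and window, again without adverse events.
- 4.17.11.5 lists each subject's assay status, titer and events of interest. It contains the information but no summary.

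**Step 3. Illustration of dilution (all rates assumed).** Let the Period 2 event risk be 0.30 if positive and 0.10 if negative at SE2 dosing, a true ratio of 3.0. Let s be the share of group (1) that is positive at SE2 dosing, and let all of group (2) still be positive.

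Group (1) risk = 0.10 × (1 − s) + 0.30 × s; apparent ratio = 0.30 / group (1) risk.

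| s | Group (1) risk | Apparent ratio |
|---|---|---|
| 10% | 0.12 | 2.50 |
| 20% | 0.14 | 2.14 |
| 30% | 0.16 | 1.88 |
| 50% | 0.20 | 1.50 |

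The share of all subjects positive at SE2 dosing who sit in group (1) also depends on q, the proportion positive at Period 1 baseline: (1 − q)s / [q + (1 − q)s].
- With q = 40% and s = 10%: 0.06 / 0.46 = 13%.
- With q = 10% and s = 50%: 0.45 / 0.55 = 82%.

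**Step 4. Antecedent subjects.** If 4.4 is applied literally, neither a sample from before first-eye surgery nor a Day 1 sample is available from the antecedent study. Under 4.17.11.1 the Period 1 baseline is then missing, so these subjects cannot enter group (1) or (2). They can still enter (3) or (4) on Period 2 data. They are 6 of about 60 planned subjects, or 10%.

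**The case against.** The strongest reply is that the table is less blind than it first appears. A reader might infer that post-SE1 converters are hidden among the negatives. The documents do not support that: such a subject meets the treatment-emergent definition and also appears in group (3), and group (1) is correctly labelled as status at Period 1 baseline. This answers the charge of concealment, but not the missing grouping, because group (3) also holds subjects who converted only after SE2.

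A reader might also infer that the trial cannot show the link at all. That goes too far, since the listing in 4.17.11.5 would let someone reconstruct status at second dosing for about 60 subjects. A hand reconstruction is not a pre-specified summary, however. Nor can it be said that the Period 2 baseline is never a grouping anywhere in the SAP; 4.17.11.2 leaves open which baseline it uses.

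The practical objection carries weight. The analysis is descriptive and no risk ratio is planned. If 12 subjects were positive and 4 had events (assumed), the Clopper-Pearson interval would run from about 10% to 65%, before any split by eye, period, window, severity or onset. A move in group (1) from 10% to between 12% and 16% would not be visible in such cells. Regrouping makes the table address the right question; it does not make the answer precise.

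On the antecedent subjects, the specific exception in 4.3 can be read as qualifying the general rule in 4.4. Inclusion criterion 6 asks for samples adequate for an immunology profile; it does not say that a sample from before the first eye exists.

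**Conclusion.** The point stands for the planned summaries. In 4.17.11.4 none of the four groups isolates assay status at second-eye dosing, and no other planned summary sets Period 2 events against it. This follows from the definitions and needs no assumed rate.

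The consequence is a possible dilution of the group (1) versus (2) contrast for Period 2 events. Its size is unknown. The fall from 3.0 to between 2.5 and 1.5 depends on the assumed 10% and 30% risks, on 10% to 50% of group (1) being positive at SE2, and on all of group (2) remaining positive. It should not be read as an estimate of what this trial will show: conversions that do not last would lower s and weaken the effect, while reversion in group (2) would narrow the contrast further.

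The 4.3/4.4 inconsistency is real but separate and smaller. It affects where six subjects are placed, not whether they can be analysed at all.

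**What to change.** 1. In SAP 4.17.11.4, for Period 2 rows, add two groups: assay negative and assay positive at the Period 2 baseline of 4.17.11.1. Do this for each assay, with ELISpot shown for REP1 and for AAV2. Keep Period 1 baseline status for Period 1 rows, and as a supportive view for Period 2.
2. Reconcile SAP 4.3 with 4.4 by stating whether the six antecedent subjects' earlier immunology results supply their Period 1 baseline. If they do not, place these subjects by Period 2 baseline only.

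The cost is a SAP wording change and one more grouping variable. No new samples are needed: Protocol 10.1.1 and Table 1 already schedule immunogenicity sampling at the Period 2 baseline, and the planned treatment-emergent derivation already requires those results. The output stays descriptive, and cells will be small, above all by surgery window.

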Both counts of subjects and events will be reported. A subject with more than one occurrence of the same AE in a particular SOC will be counted only once in the total of those experiencing AEs in that particular SOC.

If a subject experiences the same AE at more than one severity, the most severe rating will be given precedence.

If a subject experiences the same AE at more than one relationship to study drug/procedure, causal relationship will be given precedence over no causal relationship. However, where a causal relationship is identified by the Investigator, the subject will be counted once within each sub-category (Study Drug, Study Procedure, Study Drug and Study Procedure, unknown).

In the summary tables, related events are defined as events that are assessed by the investigator to be related to study drug/procedure/both or with an unknown relationship.

AEs will be assigned to Period 1 or Period 2 based on the AE Start Date. An AE with a start date on or after the day of surgery of Study Eye 2 will be attributed to Period 2; otherwise, the AE will be attributed to Period 1.

An ocular event is an event where the site of the event is reported as OU, OD or OS. Where an event is recorded as 'OU', it will be counted once for each eye (SE1 and SE2).

Separate additional summaries will be provided for adverse events classified as Ocular Inflammation and Visual Acuity Reduced. The lists of PTs assigned to Ocular Inflammation and Visual Acuity Reduced are provided in a separate document (BIIB111 Signal Detection Plan). The following summaries will be provided by eye, by period (or by surgery window), and overall:

- Ocular Inflammation-related TEAEs by SOC and PT
- Ocular Inflammation-related TEAEs by SOC and PT, and by time to onset (≤ 30 days; > 30 days)
- Visual Acuity Reduced-related TEAEs by SOC and PT
- Visual Acuity Reduced-related TEAEs by SOC and PT, and by time to onset (≤ 30 days; > 30 days)

Imputation rules for partial dates are presented in Appendix 7.1.

The following listings will be provided:

- All AEs
- AEs leading to death

AEs will be coded according the MedDRA version 23.0 or higher.

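### The Period 1 immunogenicity-safety tables group subjects by whole-study conversion, so events in subjects who convert only after the second dose are counted under treatment-emergent positive

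*SAP*

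**What the plan says.** SAP 4.17.11.4 summarises ocular inflammation, reduced visual acuity and hypersensitivity events, and eyes that have lost 15 or more letters at Month 12, under four subject groupings.

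- Groupings (1) and (2) rest on assay status at Period 1 baseline, for example "subjects with negative assay at period 1 baseline".
- Grouping (3) is "subjects with at least one treatment-emergent positive assay at any visit during the study".
- Grouping (4) is its complement, "subjects with no treatment-emergent positive assay during the study".

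To derive status for (3) and (4), "the period 1 baseline will be used to calculate the change from baseline for data in period 1 and period 2 baseline" for Period 2 data. The section then adds: "The analyses will be conducted by eye, by period and surgery window".

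Two other definitions matter. Period 1 "ends on the day prior to the day of the surgery of the second treated eye" (SAP 4.3). Events are placed by start date: "An AE with a start date on or after the day of surgery of Study Eye 2 will be attributed to Period 2" (SAP 4.17.10).

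**The concern.** Exposure status and events cover different stretches of time. Groups (3) and (4) are settled only when the last sample of the study has been read, yet the Period 1 tables count events that ended their window before the second dose. No rule requires the positive result to fall in the tabulated period or to precede the event.

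The SAP itself expects late conversion to be possible. Section 4.17.11.1 says that "second eye treatment in Period 2 in GEMINI may potentially increase the risk of a subject developing an immune response". Section 4.17.11.4 is also the only planned summary that sets assay status against inflammation and vision loss, in a study whose sample size is justified by the immunological profile of re-administration. If the Period 1 positive column is partly filled with subjects who had no response during Period 1, a real first-dose association may be hard to see.

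**Working it through.** The plan states no rate, power or effect size for this analysis, so there is no figure to reproduce. The first step is textual; the rest are illustrations.

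**1. Does any text restrict status to the period?** The baseline sentence says only which baseline each result is compared with, and it confirms that results from both periods feed the status. SAP 4.17.11.3 tabulates treatment-emergent status by visit and period, but without adverse events. SAP 4.17.11.5 provides listings. Since Period 1 closes the day before second-eye surgery, any Period 2 sample is later than the onset of any Period 1 event. The misclassification follows from the definitions.

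**2. How much of the status-defining sampling comes after the second dose?** Protocol Table 1 gives post-dose immunogenicity samples at Days 1, 7 and 14 and Months 1, 3, 6 and 12, so up to 7 per period. With k samples taken in Period 1, the share taken after the second dose is 7/(k+7):

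- second surgery between Day 14 and Month 1: k = 3, 7/10 = 70%
- between Months 3 and 6: k = 5, 7/12 = 58%
- between Months 6 and 12: k = 6, 7/13 = 54%
- after Month 12: k = 7, 7/14 = 50%

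These counts are maxima, because protocol 11.4.2 says only selected samples are analysed. A separate Period 2 baseline visit would add one sample before the second dose (for example 7/11 = 64% instead of 70%). The share varies with surgery window, which is itself a table dimension.

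**3. Late converters in group (3).** Let q1 be the assumed proportion treatment-emergent positive in Period 1, and q2 the assumed proportion of the remainder who first become so in Period 2. Everyone is taken to receive the second dose.

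- Size of group (3) = q1 + (1 - q1)q2
- Late share = (1 - q1)q2 / [q1 + (1 - q1)q2]

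About 60 subjects are planned, and 6 were treated first in an antecedent study, leaving 60 - 6 = 54 with a Period 1. At q1 = q2 = 0.20, group (3) is 0.20 + 0.80 × 0.20 = 0.36, or 19.4 subjects. Late converters are 0.16, or 8.6 subjects. The late share is 0.16/0.36 = 44%.

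**4. Effect on a Period 1 comparison.** Assume a Period 1 event risk of 30% in Period 1 converters and 10% in everyone else, a true difference of 0.20. At 20% and 20%, the risk in group (3) is (0.20 × 0.30 + 0.16 × 0.10)/0.36 = 0.076/0.36 = 0.211. Group (4) stays at 0.10, so the table shows 0.11.

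| q1 | q2 | late share of group (3) | difference shown |
|---|---|---|---|
| 0.10 | 0.10 | 47% | 0.105 |
| 0.10 | 0.40 | 78% | 0.043 |
| 0.20 | 0.20 | 44% | 0.111 |
| 0.40 | 0.10 | 13% | 0.174 |
| 0.40 | 0.40 | 38% | 0.125 |

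Over the full 10-40% grid the ranges are 13-78% and 0.04-0.17.

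**5. Selection through the second dose.** Protocol 8.3, 10.2 and 11.3 withhold second-eye treatment after severe inflammation in the first eye that does not respond to treatment. Such a subject cannot convert in Period 2. Assume no true association, a 15% Period 1 event risk, q1 = q2 = 0.20, and half of the subjects with events not dosed again.

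- Events in group (3): 0.15 × (0.20 + 0.16 × 0.5) = 0.042
- Group (3): 0.042 + 0.85 × 0.36 = 0.348, risk 12%
- Group (4): (0.15 - 0.042)/(1 - 0.348) = 0.108/0.652, risk 17%

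If every subject were dosed again, both would be 15%. The gap comes from the grouping alone.

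**The case against.** The tables are descriptive, and SAP 4.2 rules out formal comparison. The listings in 4.17.11.5 show each subject's assay status and events of interest, so order can be checked individually among about 60 subjects. Both points stand and limit the weight of the issue, but neither corrects the summary tables. It can also be argued that running the tables by period was meant to cover status as well. That is possible, but it conflicts with the wording of (3) and needs an explicit rule.

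Three stronger readings are tempting and are not supported.

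- **That the SAP attributes early events to later immune responses.** It only counts them under a column heading. It plans no causal statement and no claim that a response came first.
- **That every by-period table should use same-period status.** In Period 2 this would do harm. Under 4.17.11.3, Period 2 results are compared with Period 2 baseline. A subject who converted after the first dose and is still positive then needs a four-fold titre rise (ADA, Nabs), and an ELISpot analyte already positive cannot become emergent. Such subjects could fall into group (4) for events after the second dose. The cumulative wording suits that table.
- **That the late share of subjects is also the late share of events.** This holds only if events are unrelated to conversion. Under the 0.20 difference above, it is 0.016/0.076 = 21%, not 44%.

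**Conclusion.** The point holds for groups (3) and (4) in the Period 1 tables, where the rule as written classifies subjects by data collected after the events. Groups (1) and (2) are unaffected.

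Dilution is the general expectation, but the direction is not assured, because second dosing depends on the first-eye outcome. The two mechanisms were worked separately and not combined.

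The size rests on assumed conversion and event rates. If nearly all conversion occurs in Period 1, the effect is small. If the second dose produces many first conversions, most of the Period 1 positive column could be late converters. It is a specific defect in one set of descriptive tables and worth correcting, since those tables are the planned link between immune response and safety.

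**What to change.** In SAP 4.17.11.4, for the Period 1 tables only, define groups (3) and (4) by treatment-emergent status at Period 1 visits, that is, from samples taken before second-eye surgery. Under this rule the share of late converters in the Period 1 positive group falls to zero. Keep the cumulative whole-study status for the Period 2 and overall tables, so that subjects who converted after the first dose remain in the positive group, and state the rule for each table.

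Optionally, flag within group (3) whether each event began before or after the first treatment-emergent sample, since order within a period is otherwise still unaddressed. A footnote should say that the sample date is only an upper bound on the time of conversion: after Month 1 the samples are at Months 3, 6 and 12, so an event flagged as earlier may still have followed conversion.

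The cost is SAP wording and a little programming. Sample dates and event start dates are already collected. The downside is smaller positive groups in the Period 1 tables, for example about 11 rather than 19 subjects at the assumed 20% and 20% (0.20 × 54 = 10.8 against 19.4).
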